4.4.2. Predictors and covariates

The primary predictor is study group, i.e. Pharmacist Care or PCP Care. Covariates are other variables that could potentially mediate, moderate, or confound the association between the primary predictor and the outcomes. In this study, covariates include patient age, sex, race, ethnicity, language spoken, and comorbidities, as well as the patient's neighborhood-level SES.

4.5. Data collection.

The primary outcome will be measured via analysis of EHR records and chart review, as defined above.

For the secondary outcomes that involve medication prescription orders and fills, and for the exploratory outcomes, we will use data available from KPNC computerized sources, including HealthConnect (HC, aka EPIC) EHR data (from Clarity) and EPIC access logs. For each patient with a refill request, EHR data will be used to identify all ADHD medication prescriptions ordered and filled (sold) during the study period.

Patient care experience will be evaluated by surveying a sample of parents selected at random in both the Pharmacist Care and PCP Care groups. We have designed a short survey that takes no more than 5 to 10 minutes to complete. The survey will be fielded by email, mail, and telephone. Due to the fact that we are asking about a specific care experience and patients' recall fades quickly after 2 weeks, we will field the survey using all 3 modes in a relatively efficient sequence. A letter containing a description of the study, language regarding informed consent and confidentiality, and the survey will be sent by mail on day 7 after the secure message has been replied to, and an email with a link to the online version will be sent on day 11. Telephone administration will be attempted (up to 4 attempts total) starting on day 14 for those who have not replied to the paper or online survey. Only the first RAR will be eligible to generate a survey request. A gift card valued at \$10 to thank patients for considering participation will be included in the mailing. Responses will be treated as confidential and data will be aggregated, with no individual identifiers associated with data presented in reports.

Parent-reported outcomes will be reported on a 5-point scale and will include:

- a. Perceived effectiveness of the initial reply in addressing the request
- b. Perceived quality of care for the request overall

We will also ask parents to indicate the mode by which they would prefer to make future ADHD medication refill requests, e.g. secure message or a telephone, video, or in-person appointment.

4.6. Statistical analysis plan.

The primary analysis will treat each patient as part of the group to which their facility was assigned (intention-to-treat). However, some patients in the Pharmacist Care group might have unintentional crossover and be handled by physicians instead of pharmacists. For this reason, we will conduct a secondary analysis in which patients are grouped based on the initial management approach they actually received (pharmacist or physician, based on which type of clinician first contacted the patient), similar to a per-protocol analysis. An RAR first accessed by a pharmacist and later accessed by physician will be counted in the pharmacist group.

The primary outcome is binary, i.e., whether or not a patient who had not had a weight check in the 6 months before the refill request is referred for an appropriate follow-up visit. This will be compared between study groups using mixed effects logistic regression providing point and interval estimates of outcome odds ratios associated with study group. This analysis technique accounts for the within-facility and within-patient correlation to obtain valid estimates of treatment effects and associated standard errors. The pre-specified set of covariates for inclusion in regression models include: study group and covariates used in the randomization procedure (i.e. patient socioeconomic status (using the Neighborhood Deprivation Index), patient age, sex, race and ethnicity, and comorbidity score). Study group and other covariates will be treated as fixed effects and facility will be handled as a random effect.

In addition, exploratory/sensitivity analyses will examine the impact of including additional covariates in our estimation of treatment effect, with focus on variables with chance imbalance in distributions by treatment group, as determined in preliminary analyses. Analyses resulting in

an appreciable change in the estimate of treatment differences or increased precision of the treatment effect will be noted.

For the secondary outcomes, we will compare the days from the secure message request to prescription order or medication fill between the Pharmacist Care and PCP Care groups using linear mixed regression models, providing point and interval estimates of between-group differences in mean outcomes. If the numbers of days have a skewed distribution, log transformation will be used. Analyses of other continuous secondary outcomes will be similar. The approach to inclusion of covariates and sensitivity/exploratory analyses is as described for Aim 1.

For patient satisfaction, care experience scores will be compared between the study groups using linear mixed effects regression with log transformation if needed for skewed data, with analyses paralleling that described for the secondary outcomes. For analyses, categorical responses will be combined into a binary variable (Excellent or Very Good vs. Good, Fair, or Poor).

For all aims, secondary analyses will assess variation in the estimates of treatment effect by age, sex, socioeconomic status (using the Neighborhood Deprivation Index), and race and ethnicity, via stratification by level of the potential effect modifier. These stratified analyses will inform the fitting of mixed effects regression models with appropriate cross-product terms between the potential effect modifier and study group indicator variable, allowing for a more formal assessment of heterogeneity in treatment effect.

A facility may drop out before completion of the study if they were assigned to PCP Care but add local pharmacist management, thus diverging from their assigned group. ADHD medication refill requests to such a facility will be censored as of the dropout date (the date that local pharmacist management began).

Tests of significance will be two-tailed with an alpha of .05. No Bonferroni or other formal correction for multiple comparisons will be used, but results will be interpreted with the multiple testing issue in mind.

4.8. Sample size and power. To estimate the available sample, we extrapolated from data analyzed during the pilot period in April 2024.

Based on initial data in the pilot period, we estimate that the message pool handlers will send the regional pharmacy team 7 secure messages for straightforward ADHD medication refill requests per weekday, i.e., 35 eligible messages per week. We estimate based on expert opinion that 30% of these patients don't have a weight check in the previous 6 months. Assuming a 9-week evaluation period, the estimated sample size is 315 patients, or an average of 5 patients in each of the 63 clusters.

Given the group-randomization study design, calculation of sample sizes and minimum detectable treatment effects must account for the expected intraclass correlation (ICC) of observations within facilities. The ICCs in outcomes of interest are expected to be small, and therefore we present minimum detectable effects for an expected ICC of .03.

For Aim 1, the primary outcome is the % of patients without a weight check in the past 6 months who received referral for an appropriate follow-up visit. The following estimates assume that 30% of the 315 patients with secure messages will have not had a weight check in the past 6

months, for a sample size of 95 (63 clusters with 1.5 patients each). We also assume a desired power of 80%, a two-tailed alpha of 0.05 and an ICC of .03. If 50% of patients in the PCP Care group will receive an appropriate referral, the least detectable difference will 77%. If 80% of the patients in the PCP Care group receive an appropriate referral, the least detectable difference will be 98%. Thus, this sample size yields good power to identify only large differences between the two arms in the primary outcome.

For Aim 2, the outcome is days from the secure message to the prescription order. The following estimates assume a sample size of 315 (63 clusters with 5 patients each), a desired power of 80%, a two-tailed alpha of 0.05 and an ICC of .03. The least detectable effect size for a comparison of means will be 0.334. In other words, this study will have good power to find a statistically significant difference between the Pharmacist Care and PCP Care groups for a small to medium effect size.

For Aim 3, the outcome is perceived quality of care on the parent survey, measured on a 5-point Likert scale. We will attempt to survey all 315 parents in each of the two study groups. We estimate a response rate of 60%, for a completed sample of 189 across groups. The outcomes, effectiveness and quality scores, are measured on a continuous 5-point scale. This sample size will yield 80% power to detect effect sizes of .037 (relative to a standard deviation of 1). Thus, the survey will have good power to identify medium sized differences in perceived effectiveness and quality of care.

4. Projected Impact

This study's findings quality and timeliness of care and patient satisfaction will inform decisions about how to deploy pharmacist effort for KPNC. The study leaders include regional leaders for Virtual Medicine and Pharmacy who are well-positioned to make implementation decisions based on the results we generate.

5. Deliverables and Dissemination Plan

Our deliverables and dissemination plan have two purposes: To provide information for operational decisions by TPMG and KFH, and to establish our reputation as leaders in Desktop Medicine and Pharmacy Services through publication. Specific deliverables and plans include:

- The PI will prepare a presentation prior to study initiation to support conversations with leaders of service areas that will be included.
- Soon after the analysis of computerized data is completed, we will create an internal report for Drs. [name] and [name] to share via presentation to the appropriate chiefs and other operational leadership groups.
- The analysis of clinician and patient data will be completed after this, and we will update the internal report to support a follow-up communication.
- We will write a manuscript for submission to a peer-reviewed journal to share our findings with health care leaders in the U.S. and beyond.

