Pharmacist Management of Attention Deficit Hyperactivity Disorder
Medication Refill Requests

Study Protocol and Statistical Analysis Plan

[name], MPH, [name], [name], PharmD, E. [name], [name], MA, [name], BA, [name], MS, [name], [name], [name]

From The Permanente Medical Group (Division of Research, Virtual Care Team, Adult and Family Medicine regional leads, and TPMG Consulting Services) and Pharmacy Services, Kaiser Permanente Northern California, all in Oakland, CA

Version date: August 27, 2024

NCT06388694

Abstract

Importance. Enhancing the management of messages from patients and providing high-quality, consistent care are top priorities for The Permanente Medical Group (TPMG) and Kaiser Foundation Hospitals/Health Plan (KFH/P). A special extension of the Ryan Haight Act currently enables providers to prescribe controlled substances via telehealth interactions but expires in December 2024. Information about the quality of care provided via telehealth prescribing of controlled substances by pharmacists and primary care physicians would be helpful to inform care delivery within Kaiser Permanente and beyond.

Objective. To compare pharmacist management of refill authorization requests for attention deficit hyperactivity disorder (ADHD) medications with physician management regarding quality of care, efficiency of service, and parent satisfaction.

Design, setting, and participants. This cluster randomized clinical trial will include parents of children in Kaiser Permanente Northern California who request ADHD medication refills via secure messages from April 29 to June 28, 2024. Of KPNC's 63 facilities eligible for inclusion, we will assign 32 to Pharmacist Care and 31 to PCP Care.

Intervention. In the intervention group, a regional team of pharmacists will manage electronic refill authorization requests for ADHD medications using a standard protocol. In the comparison group, pediatricians will manage these visits using a similar protocol.

Main Outcomes and Measures. The primary outcome is whether a patient who did not have a weight recorded in the 6 months before the refill request was referred for a primary care follow-up visit. Secondary outcomes are the days from the secure message request to the prescription order and medication fill, and parent satisfaction.

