Potential Results. We will test the hypotheses that Pharmacist Care compared with PCP Care will have higher quality of care, faster time to prescriptions and fills, and higher parent satisfaction.

Potential Conclusions and Relevance. If pharmacist care for ADHD medication refill requests has better or similar outcomes compared with PCP care, this will provide evidence supporting continuation of this approach. This study's findings will be useful for KPNC and to inform discussions about renewing the special extension of the Ryan Haight Act that allows this approach.

1. Specific Aims and Hypotheses

Enhancing message management and virtual urgent care options for patients are among TPMG and KFH's top priorities. As team-based inbox management is further developed, evaluating its clinical effectiveness and outcomes in terms of patient care experience and costs will provide valuable information for operational planning. In addition, sharing what we learn with other health care systems through talks and publications will help highlight TPMG's reputation as a group that innovates to support clinicians while increasing patient access through virtual care.

This study will compare the clinical outcomes and costs of two alternative modes of management of parent requests for refills of medications for attention deficit hyperactivity disorder (ADHD): management by a regional team of pharmacists, vs. management by primary care physicians. Patients will be included if they are younger than 18 years and if their parent's

secure message request was sent to a pediatrician or family medicine physician (but not to a psychiatrist). We will conduct a cluster randomized trial in 63 facilities in Kaiser Permanente Northern California to compare Pharmacist Care with Physician Care for patients with ADHD medication refill requests with regard to:

Aim 1. Quality of care

Example hypothesis: Patients without a weight recorded in the past 6 months will be more likely to receive referral for a follow-up weight check in the Pharmacist Care group than the Physician Care group.

Aim 2. Timeliness of care

Example hypothesis: Patients managed via Pharmacist Care will have a faster time to refill prescription than those managed via Physician Care.

Aim 3. Parent satisfaction

Example hypothesis: Parents in the Pharmacist Care group will report comparable satisfaction with the process compared with the Physician Care group.

2. Background and Significance

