The regional pharmacy team started to handle free-text secure message requests for refills from parents of patients with PCPs in pediatrics during a pilot period starting April 11, 2024. Secure messages are different from RARs because they contain free text. These were found to be difficult to flag and send to the regional pharmacy team because accurately identifying the relevant secure messages required manual handling. The rate of such messages that could be identified per day would not have reached the intended sample size for this study. Thus, this study was designed to focus only on RARs, which are much simpler to identify consistently. The regional desktop medicine leader sent an email to the pediatric department at every facility to ask that during the study period, they ignore RARs from facilities randomized to Pharmacist Care, but continue to handle RARs from facilities randomized to Physician Care.

The formal study period will include patients with secure messages sent to the regional pharmacy team from May 6, 2024 to June 21, 2024 (7 weeks). The unit of analysis will be the RAR, allowing some patients to appear up to two times in the study cohort.

4.2. Intervention.

All procedures will be conducted as part of standard of care. In the Pharmacist Care group, each RAR for an ADHD medication will be assigned to a pharmacist on the regional team. Pharmacists will review requests using a standard protocol. They will call parents via telephone to elicit additional information where needed, file ADHD medication prescriptions where appropriate, and send follow-up secure messages.

In the PCP Care group, each ADHD medication RAR will be sent to the PCP. Physicians will review requests using the standard regional protocol (as well as any existing medical center-level protocols). Following this protocol, physicians call patients via telephone to elicit additional information where needed, file ADHD medication refill prescriptions when appropriate, and send follow-up secure messages.

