4.4. Main outcomes and measures

4.4.1. Outcomes

The primary outcome will be measured only among patients who have not had a weight recorded in the EHR during the 6 months (180 days) prior to the ADHD medication refill request. We will determine whether the prescribing clinician attempted to ensure that the child had a weight checked or recorded, counting the outcome as present if (a) the patient was referred for an in-person visit for a weight check (including a well child visit or a nurse visit for a weight check), or (b) had a parent-reported weight recorded in the EHR. This outcome will be assessed via analysis of EHR data and chart review. Referral for a visit or weight check (part a above) will include any of the following:

- (a) the EHR record or chart review indicates that an appropriate in-person appointment was booked with pediatrics, family medicine, or psychiatry after the pharmacist or PCP handled the message;
- (b) a chart note indicates that the pharmacist or physician handling the RAR instructed the parent to schedule a follow-up appointment for a weight check;
- (c) a note in the EHR indicates that a medical assistant or other staff member had attempted to book a follow-up appointment for a weight check

Secondary outcomes will be the:

- a. Whether the child had a weight recorded within 30 days after the RAR, regardless of the reason for the weight being measured (this measure would count weights recorded at urgent visits)
- b. Hours from the secure message request to the prescription order being placed, among patients who had a prescription ordered
- c. Days from the secure message request to the prescription being filled (sold), among patients who had a prescription ordered
- d. Parent satisfaction with care, as measured by standardized survey items

Exploratory outcomes will be:

- a. Whether the provider initially handling the request was able to fully resolve it without referring it to another provider (first-touch resolution)
- b. Whether the patient had a refill prescribed (% of patients with refills prescribed)

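### Time to fill has no stated capture end beyond the request window, and prescriptions ordered but never filled drop out of its analysis

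*Combined protocol and SAP*

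**What the plan says.** Data collection (section 4.5): "EHR data will be used to identify all ADHD medication prescriptions ordered and filled (sold) during the study period". No number of days per request and no run-out date is given.

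Study period: section 4.1 includes "patients with secure messages sent to the regional pharmacy team from May 6, 2024 to June 21, 2024 (7 weeks"), while the abstract speaks of parents "who request ADHD medication refills via secure messages from April 29 to June 28, 2024". Both are windows for sending requests, and they differ.

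Outcomes (section 4.4.1): secondary outcome (c) is "Days from the secure message request to the prescription being filled (sold), among patients who had a prescription ordered". By contrast, secondary outcome (a) has its own window: "Whether the child had a weight recorded within 30 days after the RAR". Exploratory outcome (b) is "Whether the patient had a refill prescribed (% of patients with refills prescribed"); no outcome gives the proportion filled.

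Analysis (section 4.6): times to order and fill are compared with linear mixed models, log-transformed if skewed. The only censoring rule concerns facilities that leave the PCP Care arm. The abstract's hypotheses for Pharmacist Care are "higher quality of care, faster time to prescriptions and fills, and higher parent satisfaction".

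**The concern.** There are two separate problems.

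**Capture window.** If fills count only when they fall inside the request window, a request on May 6 has about seven weeks for its fill to be seen and one on June 21 has almost none. Late requests then supply only short times. More records are lost where fills are slower or more spread out, so the comparison of arms is biased, not just less precise.

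**Unfilled prescriptions.** The outcome's denominator is patients with an order, but a linear model of days has no value for a prescription that was never filled. The analysed set shrinks to those with a fill. If one arm leaves more prescriptions unfilled, neither the timing result nor any other listed outcome shows it.

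At stake is the reading of time to fill, a secondary outcome with a stated directional hypothesis.

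**Working it through.** **The plan's own figure.** Section 4.8 gives a least detectable effect of 0.334 SD for time to order: N = 315, 63 clusters of 5, ICC 0.03, 80% power, two-sided alpha 0.05. The design effect is 1 + (5 − 1) × 0.03 = 1.12, and (1.960 + 0.842) × √(4 × 1.12 / 315) = 0.334. It reproduces. It concerns orders and takes all 315 requests to yield a time.

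**Effect of a literal cut-off.** The documents give no times to order or fill, so every distribution here is assumed. Requests are spread evenly over T days, and an event is seen only if request day + t ≤ T. A time t then has weight (T − t)/T. May 6 to June 21 gives T = 26 + 21 = 47. Log-SD is in brackets for lognormal cases; the ratio is of geometric means, slower-labelled arm over the other.

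| Assumed arms (mean days) | True difference | Observed difference | True ratio | Observed ratio |
|---|---|---|---|---|
| Exponential 3 vs 5 | 2.00 | 1.61 | 1.67 | 1.58 |
| Lognormal 3 (1.2) vs 5 (1.2) | 2.00 | 1.22 | 1.67 | 1.57 |
| Lognormal 3 (1.2) vs 5 (0.5) | 2.00 | 2.37 | 3.02 | 3.22 |
| Lognormal 3 (0.5) vs 5 (1.2) | 2.00 | 0.74 | 0.92 | 0.80 |
| Lognormal 3 (1.2) vs 3 (0.5) | 0.00 | 0.48 | 1.81 | 1.96 |
| Exponential 0.5 vs 1 (order-like) | 0.50 | 0.48 | 2.00 | 1.98 |
| Lognormal 0.5 (1.2) vs 1 (1.2) (order-like) | 0.50 | 0.45 | 2.00 | 1.97 |

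- Records lost for 3 vs 5 days: 6.4% and 10.6% (exponential), 6.3% and 10.2% (lognormal, log-SD 1.2).
- With the abstract's dates, T = 2 + 31 + 28 = 61, and 3 vs 5 gives 1.71 (exponential) and 1.34 (lognormal), with ratios 1.61 and 1.59.
- On the log scale the differently shaped arms move by 3.22/3.02 = 1.07, 0.80/0.92 = 0.87 and 1.96/1.81 = 1.08, that is, by about 7%, 13% and 8%.

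**Run-out of 30 days after the last request.** The weight becomes the smaller of 1 and (T + 30 − t)/T. Compare keeping every fill seen by then with discarding fills after day 30 of each request (raw differences in days, T = 47):

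| Assumed arms | True | Keep all fills to day 30 after last request | Discard fills after day 30 |
|---|---|---|---|
| Exponential 3 vs 5 | 2.00 | 1.99 | 1.93 |
| Lognormal 3 (1.2) vs 5 (1.2) | 2.00 | 1.68 | 1.41 |
| Lognormal 3 (1.2) vs 5 (0.5) | 2.00 | 2.12 | 2.26 |
| Lognormal 3 (0.5) vs 5 (1.2) | 2.00 | 1.56 | 1.15 |
| Lognormal 3 (1.2) vs 3 (0.5) | 0.00 | 0.12 | 0.27 |

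Keeping all observed fills is closer to the truth in every row.

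**Never filled.** Assume 5% vs 15% unfilled and exponential times with mean 3 days otherwise. The planned difference among filled prescriptions is 0. By day 30, 95% vs 85% are filled. With 3 × (1 − e^(−10)) = 3.00, the 30-day restricted means are 0.95 × 3.00 + 0.05 × 30 = 4.35 and 0.85 × 3.00 + 0.15 × 30 = 7.05 days.

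**The case against.** The literal cut-off may never be applied. Weights are needed for 30 days after each request, and survey mailing, email and calls start 7, 11 and 14 days after the reply. The title block carries "Version date: August 27, 2024", which is 67 days after June 21. Collection after the last request was clearly planned for other outcomes, so the wording on orders and fills may simply be loose. This stands: the truncation bias is conditional on how the sentence is followed. But the sentence is the only capture rule given for orders and fills, and an analyst who departs from it must choose an end date.

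A reader might infer from the raw-mean figures that the cut-off could halve a difference or manufacture one. For data that skewed, section 4.6 prescribes a log transformation, and there the shifts are modest. In the equal-means case the arms already differ 1.81-fold on the log scale, so truncation enlarges a difference that exists.

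A reader might also infer lost power for Aim 2. The power calculation is for time to order, which barely moves if orders take about a day or less. Truncation does not always cost power either: in the lognormal 3 vs 5 case the standardised raw effect rises from 0.270 to 0.312.

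On unfilled prescriptions, it is fair to say that a time outcome answers how long filling took, that the 5% vs 15% split has no source in the documents, and that the restricted-mean gap comes largely from giving unfilled prescriptions 30 days. That records without a fill date drop out is inferred from the model, not stated. What remains is that the outcome's denominator includes these patients, no rule covers them, and nothing listed reports them.

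**Conclusion.** The point holds as a cheap improvement to a secondary outcome. As written, the capture rule right-truncates time to fill; whether it would be applied that way is uncertain. For fill times averaging 3 and 5 days with the same shape in both arms, it would shrink a raw difference by about 20% (exponential) to 39% (lognormal), but the log-scale ratio by only about 5% to 6%. With differently shaped lognormal arms the ratio shifts by about 7% to 13%, in either direction. All of this rests on assumed times and evenly spread requests. If the arms have the same fill-time distribution, the cut-off produces no difference.

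The gap on unfilled prescriptions does not depend on how the study period is read. Its size is unknown, and it matters only if the share unfilled differs between arms.

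The documents do not support a claim that the trial's main conclusion or Aim 2's powered comparison is compromised.

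**What to change.** 1. In section 4.5, replace the reference to the study period with capture of orders and fills through at least 30 days after the last RAR: July 21, 2024 for an RAR on June 21. Keep all observed fills in the planned mixed model. Reconcile the study dates in the abstract and section 4.1; if June 28 stands, the date becomes July 28.
2. Report by randomised arm the proportion of ordered prescriptions, and of all RARs, filled within 30 days of the RAR, alongside the exploratory proportion prescribed.
3. Add a sensitivity analysis of time to fill among ordered prescriptions: a time-to-event or 30-day restricted-mean comparison that allows for facility clustering, with prescriptions still unfilled at day 30 censored there.

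The cost is a few sentences, one added analysis and possibly a later extract from the same EHR source; the documents do not say when data are drawn, so none may be needed. July 21 is 37 days before the version date (10 days in July plus 27 in August), and July 28 is 30 days before it. The planned main model is unchanged.

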Pharmacist management of secure messages from patients is innovative in not having been adopted or evaluated at large scale. Preliminary anecdotal and unpublished information from within TPMG suggests that pharmacists' scope of practice is well-suited to message management for many specific conditions based on treatment algorithms. At our KP San Francisco medical center, pharmacists have been able to take charge of messages for a range of issues, including refill authorization requests and requests to manage chronic conditions (hypertension, osteoporosis, attention deficit disorder, gout) and time-limited conditions (sexually transmitted infections, latent tuberculosis, opioid tapering, and assessment of Paxlovid eligibility).

4. Approach

4.1. Design, setting, and participants.

This cluster randomized clinical trial will assign parent secure message requests to pediatricians or family medicine physicians for ADHD medication refills for children aged <18 years to either Pharmacist Care or Physician Care. The unit of randomization is the KPNC facility. KPNC is an integrated health care system with 4.5 million members served by more than 9700 physicians and 90,000 employees in 21 hospitals and 207 medical offices. It has a mature EHR (EPIC/HealthConnect, adopted circa 2008) and encourages members to use a wide array of options for outpatient care, including secure messages to physicians via the EHR portal, e-visits, video, telephone, and in-person office visits.

The target population is children and adolescents aged <18 years whose parents send a refill authorization request (RAR) for an ADHD medication to their child's pediatrician. An RAR is a highly structured electronic communication that does not allow the requestor to add any free text. This structure makes it possible for either a pharmacist or physician to handle the RAR.

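### The facility-only random effect leaves out pharmacists who probably serve several facilities, so standard errors for the two timing outcomes may be too small if the regional team is small and its members differ in speed

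*Combined protocol and SAP*

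**What the plan says.** Section 4.1: "The unit of randomization is the KPNC facility". The Abstract gives the split: "we will assign 32 to Pharmacist Care and 31 to PCP Care". Under section 4.2, in the Pharmacist Care arm "each RAR for an ADHD medication will be assigned to a pharmacist on the regional team", whereas in the PCP Care arm each request goes to the patient's own physician.

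In section 4.6 the paragraph on the primary outcome names the random effects: "Study group and other covariates will be treated as fixed effects and facility will be handled as a random effect". It says of the method: "This analysis technique accounts for the within-facility and within-patient correlation to obtain valid estimates of treatment effects and associated standard errors". The timing outcomes are to be compared "using linear mixed regression models, providing point and interval estimates of between-group differences in mean outcomes", with a log transformation if the data are skewed. No pharmacist or provider term appears anywhere, nor a provider-level sensitivity analysis. Section 4.6 also expects that "some patients in the Pharmacist Care group might have unintentional crossover and be handled by physicians instead of pharmacists".

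For Aim 2, section 4.8 works from these inputs: "sample size of 315 (63 clusters with 5 patients each), a desired power of 80%, a two-tailed alpha of 0.05 and an ICC of .03". It gives a least detectable effect of 0.334 SD.

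**The concern.** The two arms are clustered differently. PCPs presumably sit within facilities, so a facility effect picks up most of the correlation among requests that share a physician. A regional pharmacist probably handles requests from several of the 32 Pharmacist Care facilities. A fast or slow pharmacist then shifts many facilities together. A facility intercept estimates its variance from differences between facilities, so it cannot see a shift that they share.

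The Pharmacist Care mean may thus rest on the working habits of a few people, while the model treats it as resting on 32 independent facilities. Timeliness is a stated aim. Section 4.8 claims good power for small to medium timing effects but only for large differences in the primary outcome, and section 4.6 applies no multiplicity correction. A significant timing result could therefore become prominent, and the Abstract wants the findings to inform care beyond Kaiser Permanente.

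**Working it through.** **Inputs from the documents.** 32 and 31 facilities (Abstract); 5 requests per facility, facility ICC 0.03, 80% power, two-sided alpha 0.05 (section 4.8). This gives 32 × 5 = 160 and 31 × 5 = 155 requests.

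**Assumed inputs.** The number of pharmacists K and the pharmacist ICC ρ are not given. Pharmacists are taken to carry equal loads spread across facilities, with total variance held at 1.

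**Step 1: reproduce the plan's figure.**
- Design effect = 1 + (5 − 1) × 0.03 = 1.12.
- Variance of the difference V0 = 1.12 × (1/160 + 1/155) = 0.01423, so SE = 0.1193.
- Least detectable effect = (1.960 + 0.842) × 0.1193 = 0.334.

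This matches the plan. The figure is correct for facility clustering alone.

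**Step 2: add pharmacist variance in the Pharmacist Care arm.**
- V1 = V0 + ρ × (1/K − 1/160).
- SE ratio R = √(V1/V0).
- Type I error of the facility-only test = 2 × [1 − Φ(1.96/R)].
- Least detectable effect = 2.802 × √V1.

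Example, K = 5 and ρ = 0.03: the added variance is 0.03 × (0.2 − 0.00625) = 0.00581, V1 = 0.02004 and R = 1.187. Type I error is 9.9%, the least detectable effect is 0.397, and power at 0.334 is 66%.

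| K | ρ | SE ratio | Type I error | Least detectable effect | Power at 0.334 |
|---|---|---|---|---|---|
| 4 | 0.03 | 1.23 | 11.1% | 0.411 | 62% |
| 4 | 0.05 | 1.36 | 15.0% | 0.455 | 54% |
| 5 | 0.03 | 1.19 | 9.9% | 0.397 | 66% |
| 5 | 0.05 | 1.30 | 13.1% | 0.433 | 58% |
| 10 | 0.03 | 1.09 | 7.3% | 0.366 | 73% |
| 10 | 0.05 | 1.15 | 8.9% | 0.385 | 68% |
| 20 | 0.03 | 1.05 | 6.1% | 0.349 | 76% |
| 20 | 0.01 | 1.02 | 5.4% | 0.339 | 79% |

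With ρ = 0 there is no error.

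**Step 3: check by simulation.** 20,000 trials per setting, random intercept for facility, t test on 61 df. Type I error was 4.6% with no pharmacist variance. At ρ = 0.03 it was 9.2% (K = 5), 6.8% (K = 10) and 5.8% (K = 20); at ρ = 0.05 with K = 5 it was 12.5%. The mean model SE stayed near 0.120 throughout. At K = 5 the true SD of the estimate was 0.141 (ρ = 0.03) and 0.155 (ρ = 0.05). The facility effect does not absorb the pharmacist variance.

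**Step 4: two departures from these inputs.**
- *Crossover.* If a share c of the arm is handled by physicians, the added variance becomes ρ × [(1 − c)²/K − (1 − c)/160]. With an assumed c = 0.20, K = 5 and ρ = 0.03, this is 0.03 × (0.128 − 0.005) = 0.00369, and type I error falls from 9.9% to 8.1%.
- *Fewer requests.* Section 4.8 uses 9 weeks, but section 4.1 gives a 7-week study period: 7 × 35 = 245 requests, 3.89 per facility. Then V0 = 1.0867 × (1/124.4 + 1/120.6) = 0.01775 and, at K = 5 and ρ = 0.03, V1 = 0.02351. Type I error is 8.9%. Limiting the timing outcomes to requests with a prescription ordered works in the same direction.

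**Step 5: primary outcome.** A simulated random-intercept logistic analysis with 95 patients (500 trials per setting) gave at most 7% type I error for a handler ICC up to 0.10.

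**The case against.** The strongest reply concerns the target of inference. Facilities are the randomized unit. If the question is whether this regional team is faster than the PCPs, a team that happens to be fast is a real effect, and facility-level standard errors are defensible. The type I errors above imagine a new set of pharmacists in each trial. The plan's operational aim, deciding whether to continue this service, fits the narrower target. This stands, but the plan does not confine itself to that target: it also addresses health systems elsewhere and the renewal of a federal rule.

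A reader might infer that the standard errors are definitely too small. The documents do not support that. It requires pharmacists who differ and a team that is small relative to about 160 requests, and neither is documented. A shared standard protocol may keep differences low.

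A reader might also infer that every Pharmacist Care request is handled by this team. Section 4.2 says so by assignment only. Section 4.2 also concedes that these requests still reach PCP inboxes, and section 4.6 expects crossover. That each pharmacist serves several facilities is inferred from the team being regional, since no allocation rule is given.

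Finally, the random-effects sentence sits in the primary-outcome paragraph. Facility-only timing models are the likely reading, not an explicit statement, though no other random effect is named for timing.

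**Conclusion.** The concern holds conditionally. The stated model and the power calculation omit a likely second source of clustering in the Pharmacist Care arm, so the claim of valid standard errors in section 4.6 does not cover it. Over a pharmacist ICC of 0.03 to 0.05, type I error for the timing outcomes is about 10 to 15% with 4 or 5 pharmacists. At ICC 0.03 it is about 7% with 10 and about 6% with 20. Crossover and a smaller sample reduce these figures. They bear on conclusions about pharmacist management beyond this team; for this team alone, the planned analysis can stand. The 0.334 figure is not an arithmetic error, and the primary outcome is little affected. The point therefore concerns two secondary outcomes, and its size depends on facts that the sponsor holds and the documents do not give.

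**What to change.** Keep the facility model as planned. For request-to-order and request-to-fill times, pre-specify a sensitivity analysis that adds a random effect for the pharmacist who first handled the request, identified from the EPIC access logs already listed as a data source in section 4.5. Cross this effect with facility in the Pharmacist Care arm and use Satterthwaite or Kenward-Roger degrees of freedom. Arms stay as randomized, and requests first handled by a physician carry no pharmacist effect.

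Report this interval beside the facility-only interval, with the number of pharmacists and how requests were shared among them. State that the variance component is poorly estimated when pharmacists are few: in a simulation of a crossed handler model with 4 pharmacists, it was estimated as zero in 20 to 30% of trials, which returns the facility-only answer. Agreement between the two intervals is then weak reassurance.

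If this analysis is not reported, limit the timing conclusion to this regional pharmacist team. The cost is one extra model per timing outcome from data already held, and wider timing intervals if the team is small. Trial conduct does not change.
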